6.5. Safety Set

All participants who received at least 1 dose of ALXN1840.

6.6. Pharmacokinetic Analysis Set

All participants who have sufficient plasma samples to enable the calculation of PK parameters and provide PK profiles.

6.7. Pharmacodynamic Analysis Set

All participants who have sufficient plasma samples to enable the calculation of PD parameters and provide PD profiles.

7. STATISTICAL ANALYSIS

Summary statistics will be computed and displayed by visit where applicable and will be presented by cohort (treatment experienced/treatment naïve), and overall. Descriptive statistics for continuous variables will minimally include the number of participants, mean, standard deviation (SD), minimum, median, and maximum. For categorical variables, frequencies and percentages will be presented. If the number of participants is deemed to be too small, descriptive statistics might not be presented and only listings will be presented. Graphical displays will be provided as appropriate.

Analyses will be performed using the Statistical Analysis Software[®] (SAS[®]) Version 9.4 or higher (SAS Institute Inc., Cary, North Carolina).

7.1. Study Participants

7.1.1. Disposition of Participants

The number and percentage of all participants screened, enrolled, included in the Full Analysis (FA), Per-Protocol (PP), Safety, PK, and PD analysis sets will be summarized. The reasons for exclusion from the analysis sets will also be provided. Frequency counts and percentages of participants excluded prior to enrollment will be provided for participants who failed to meet study entry requirements during Screening.

The number and percentage of participants who completed, or prematurely discontinued from the study will be summarized by cohort and overall. For participants who discontinued the study, the number and percentage will be summarized by their reason for premature discontinuation. Additionally, the number of participants who completed or prematurely discontinued treatment and the reason for treatment discontinuation will be summarized. A summary of participants who did not meet inclusion or who met exclusion criteria will be provided.

Descriptive statistics of the number of days in the study will be summarized. The date of first and last use of the study drug, and the study termination date will be listed. Individual reasons for premature discontinuation from the study will be presented in a listing, as will the reason for premature discontinuation from study treatment. All enrolled participants will be listed indicating their membership to each analysis set along with the reason for exclusion. Additionally, a listing of the inclusion/exclusion criteria and a listing of participants and the inclusion criteria they failed to meet and the exclusion criteria they met will be provided. A listing of screen failure participants will also be provided.

7.1.2. Protocol Deviations

All important/not important protocol violations will be determined and appropriately categorized prior to database lock. The number and percentage of participants with any important/not important protocol violations as well as the number and percentage of participants with violations within each category will be presented. A listing will also be provided.

7.1.3. Demographics, Disease Characteristics, and Medical History

All demographic and Baseline characteristics information will be summarized on the FA Set. Summary statistics will be presented by cohort and overall. Continuous variables will be

presented using descriptive statistics, and categorical variables will be presented using frequencies and percentages. Age will be calculated relative to signing of informed consent and will be summarized as both a continuous and categorical variable. Listings will also be provided.

7.1.3.1. Demographics

The following demographic variables will be summarized:

- Sex
- Race (where collection is permitted by local regulations)
- Ethnicity (where collection is permitted by local regulations)
- Age (years)
- Height (cm)
- Weight (kg)
- Body mass index (BMI) (kg/m²)

7.1.3.2. Baseline Disease Characteristics

The following Baseline characteristics will be summarized:

- Time since WD diagnosis
- Cumulative duration of prior WD treatment
- Cirrhosis
- LBC (µmol/L)
- LBC categorization based on normal reference range (low: <0.7 µmol/L for female, <0.9 µmol/L for male; normal: 0.7 to 5.9 µmol/L for female, 0.9 to 4.4 µmol/L for male; high: >5.9 µmol/L for female, >4.4 µmol/L for male)
- Calculated NCC (µmol/L)
- NCC categorization based on normal reference range (<0.8 µmol/L, 0.8 to 2.3 µmol/L, >2.3 µmol/L)
- Directly measured NCC (µmol/L)
- Albumin (g/L)
- International normalized ratio (INR)
- Total bilirubin (µmol/L)
- Direct bilirubin (µmol/L)
- Alanine aminotransferase (ALT) (U/L)
- Aspartate aminotransferase (AST) (U/L)
- Gamma glutamyltransferase (GGT) (U/L)

- Platelets ($10^9/L$)
- Leukocytes ($10^9/L$)
- Creatine kinase (U/L)
- Hemoglobin (g/L)
- Total plasma copper ($\mu\text{mol/L}$)
- Total plasma copper categorization based on normal reference range (low: $< 11.33 \mu\text{mol/L}$ [$< 720 \text{ ng/mL}$]; normal: $11.33 - 26.12 \mu\text{mol/L}$ [$720 - 1660 \text{ ng/mL}$]; high: $> 26.12 \mu\text{mol/L}$ [$> 1660 \text{ ng/mL}$])
- PUF copper ($\mu\text{mol/L}$)
- CpC ($\mu\text{mol/L}$)
- Total plasma molybdenum ($\mu\text{mol/L}$)
- PUF molybdenum ($\mu\text{mol/L}$)
- Cp ($\mu\text{mol/L}$)
- 24-hour urinary copper ($\mu\text{g/day}$)
- 24-hour urinary molybdenum ($\mu\text{g/day}$)
- Categorization of Baseline lab values (ALT, AST, GGT, platelets, leukocytes, creatine kinase) based on the reference ranges (L: Low, N: Normal, H: High)

7.1.3.3. Medical/Surgical History, and WD History

Medical and surgical history will be summarized by counts and percentages and displayed by System Organ Class (SOC) and Preferred Term (PT) within each SOC. Both SOC and PTs will be coded using Medical Dictionary for Regulatory Activities (MedDRA), Version 22.0 or higher, available at the start of the study. This dictionary will be used throughout the life of the study and will not be updated during the study conduct. The number and percentage of participants will be presented for ongoing conditions and previous conditions separately by SOC and PT. A listing will also be created.

All details of WD diagnosis will be listed in full.

7.1.4. Prior and Concomitant Medications/Therapies

Prior medications will be defined as medications that were discontinued prior to the start of study drug. Concomitant medications will be defined as medications that either started prior to first dose of study drug and were continuing at the time of first dose of study drug or started on or after the date of the first dose of study drug. If it cannot be determined whether a medication was stopped prior to the start of study drug dosing due to partial or missing medication start or end dates, it will be considered a concomitant medication.

The World Health Organization (WHO) Drug Dictionary version from March 2018 or later will be used to code the medications. Medications will be summarized by Anatomical Therapeutic Chemical (ATC) level 3 class and generic drug name.

Prior and concomitant medications will be summarized separately for the FA Set by cohort and overall. The number and percentage of participants receiving any concomitant medication will be summarized, as well as the number and percentage receiving any concomitant medication by ATC drug class and generic drug name. Participants reporting use of more than 1 medication at each level of summarization (any medication received, ATC class, and generic drug name) will be counted only once. All ATC class terms will be displayed alphabetically and generic drug names within each ATC class will be displayed by descending order of incidence. Prior medications used to treat WD and an additional analysis of all prior medications will be summarized similarly. WD treatment history will be summarized by counts and percentages for Cohort 1 and Cohort 2 by prior WD medication, where prior WD medication is defined as the later of the treatment at the time of Screening or most recent treatment prior to Screening and is categorized as penicillamine, trientine hydrochloride, zinc, or combination.

Prior and concomitant medications will be presented in a data listing by patient and medication name.

7.2. Efficacy Analyses

The analyses and summaries will be based on the FA Set. For by-visit analyses, the definition is given in Appendix 9.2. Listings will also be provided for all efficacy assessments.

7.2.1. Primary Analysis

Based on the ALXN1840 mechanism of action, the primary objective of this study is to demonstrate a net negative copper balance with daily repeat-dose ALXN1840 treatment (15 mg and 30 mg) in participants with WD.

The primary analysis will be performed using the FA Set. Average daily copper balance and molybdenum balance will be calculated over the following periods:

- Day -4 through Day -1 representing pre-dose Baseline
- Days 1 through 8 representing the ALXN1840 15 mg/day accumulation period
- Days 25 through 28 representing the ALXN1840 15 mg/day steady-state period
- Days 31 through 35 representing the ALXN1840 30 mg/day accumulation period
- Days 36 through 39 representing the ALXN1840 30 mg/day steady-state period

Copper balance is defined by the difference in copper input and copper output. A negative Copper balance will indicate greater copper output than copper intake. Copper input is defined as the sum of all copper input as measured in all food and fluids over the specified period. Copper output is defined as the sum of all copper output as measured in urine and feces over the specified collection period. Many of the copper inputs and outputs will be collected with technical replicates and the mean of the replicates will be utilized in the analysis. The average daily copper balance is calculated as the difference in copper input and copper output during the specified period, divided by the total number of days in that period.

As ALXN1840 is expected to increase copper excretion through fecal excretion, copper in stool will be critical for determining copper balance. Because the timing of bowel movements can be irregular, assessment of copper and molybdenum balance will only include data up to the day of

the final bowel movement. For example, if the participant does not have a bowel movement on Day 8, then average daily copper balance for the Day 1 through Day 8 period will only include data from Day 1 through Day 7.

In the case of the 15 mg/day steady-state period (ie, Day 25 through Day 28), stool data collected on Days 29 - 30 samples may be used if needed to support assessments for the 15 mg/day dose. Use of these stool data (as needed) are consistent with an approximately 2-day gastrointestinal transit time.

In the case of stool irregularity, and to support assessment of copper output over time, bowel movement copper and molybdenum outputs may be averaged over the days between bowel movement (or start of study) to ensure an approximate value for each 24-hour period.

The daily copper balance for each subject will be plotted as will the mean daily copper balance.

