
Safety Evaluate the safety and tolerability of repeated-dose administration of ALXN1840 15 mg/day and 30 mg/day in participants with WD
	
Safety parameters:
 
 • Treatment emergent adverse events (TEAEs)/serious adverse events (SAEs) • Clinical laboratory assessments (serum chemistry, hematology, coagulation, and urinalysis) • Physical examinations • Heart rate, intervals (PR, QRS, QT and QTc), and clinically significant electrocardiogram (ECG) findings as determined by triplicate 12-lead ECG • Vital sign assessments (blood pressure and heart rate)

Exploratory Determine dose response of ALXN1840 15 mg/day and 30 mg/day for copper balance in participants with WD
	Assess dose response of ALXN1840 on copper balance focusing on copper balance
Determine the effect of treatment duration on copper balance in participants with WD	Determine the effect of time following initiation of ALXN1840 treatment on copper balance
Assess the effects of ALXN1840 on ceruloplasmin, ceruloplasmin-bound copper, LBC profiles in plasma in participants with WD	Ceruloplasmin, ceruloplasmin-bound copper, and LBC: Change in ceruloplasmin at Days 1, 8, 25, 29, 36, and Day 39 compared with predose

Objectives	Endpoints
Assess dose proportionality at steady state of doses of ALXN1840 15 mg/day and 30 mg/day in participants with WD	Based on PK parameters
Assess effects ALXN1840 on copper:molybdenum ratio in plasma at steady state in participants with WD	Measure plasma copper:molybdenum ratios at steady state compared with predose
Assess the effects of repeat-dose ALXN1840 on copper:molybdenum ratio in urine and feces in participants with WD	Mean daily copper:molybdenum ratio in urine and feces at steady state compared with predose baseline

Note: The accumulation period refers to time from initiation of ALXN1840 (Day 1) to expected steady state at Day 10, based on 5 times the half-life of 2 days.

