 - Day 1 through Day 8 (Input/Output (I/O) for 15 mg)
 - Day 25 through Day 39 (Days 25 through 28, I/O for 15 mg; Days 29 through 39, I/O for 30 mg)

5. During these periods all intake (including food and drink) and output (including urine and feces) will be collected and assessed for copper and molybdenum.

Abbreviations: AP = accumulation period; EOS = End of Study; SS = steady state.

Participants who are taking copper-chelating therapies (penicillamine or trientine) at the time of enrollment will be discontinued from their decoppering therapies starting on Day -4 to allow a Baseline assessment of copper/molybdenum balance prior to ALXN1840 treatment. On Day 1, participants will be initiated on 15 mg/day of ALXN1840 for a Treatment Period of approximately 28 days followed by titration up to 30 mg/day on Day 29. Before titration to 30 mg/day, the SRC will review available safety data through Day 23 for each participant.

Participants will have intake and output collection periods from Day -4 through Day -1, from Day 1 through Day 8, and Day 25 through Day 39. The collection periods will support an assessment of both copper and molybdenum balance (as a measure of ALXN1840 absorption, distribution, metabolism, and excretion [ADME]) at the 15 mg and 30 mg doses and will allow assessment of the effects of duration of treatment on copper elimination and copper balance.

Collection periods for feces and urine will vary in duration from 3 to 15 days to support assessment of both copper and molybdenum balance before and at steady state for both 15 mg and 30 mg. Equilibration periods on copper/molybdenum-controlled diets will be a minimum of 48 hours. Copper balance will be calculated as the mean daily copper balance over each of the 4 collection periods. The interpretation of copper balance will be based on the criteria established by Hill (1986) when undertaking copper balance studies with zinc treatment. For assessment of ALXN1840 effect on copper balance, the time period for analysis will take into consideration the average bowel transit of approximately 40 hours (male: 33 hours; female: 47 hours) (Camilleri, 1986; Metcalf, 1987).

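### The 15 mg accumulation window opens on Day 1 with no bowel-transit lag, while the 30 mg window opens two days after the dose change, so any true fecal effect in Days 1-8 is attenuated by about 17-25%

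*SAP*

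**What the plan says.** SAP Section 4 states that "the time period for analysis will take into consideration the average bowel transit of approximately 40 hours (male: 33 hours; female: 47 hours"). Protocol 4.1 and 4.2 say the same.

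SAP 7.2.1 and Protocol 9.4.1 then list the same balance windows. Three matter here:

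- The first is "Days 1 through 8 representing the ALXN1840 15 mg/day accumulation period". It lasts eight days and opens on the day of the first dose.
- The second is the steady-state window at 15 mg, the four days from Day 25 to Day 28.
- The third is "Days 31 through 35 representing the ALXN1840 30 mg/day accumulation period". It lasts five days.

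Dosing at 15 mg starts on Day 1 and dosing at 30 mg on Day 29. Days 29-30 lie in neither 30 mg window. Stool from those two days may, if needed, count towards the 15 mg steady-state period, and the reason given is: "Use of these stool data (as needed) are consistent with an approximately 2-day gastrointestinal transit time".

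Copper output is whatever urine and feces are measured within the window dates. Two further rules concern stool timing. One ends a window at the last bowel movement. The other allows stool copper to be averaged over the days between bowel movements.

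**The concern.** The two accumulation windows stand differently to the dose that they represent: one opens on the first day of that dose, the other 48 hours later. Under the two-day transit that the plan itself invokes, stool passed on Days 1-2 mostly reflects the untreated run-in, yet it is counted as 15 mg output.

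Neither stool rule repairs this. The last-bowel-movement rule trims only the end of a window. Averaging between bowel movements spreads stool over days but does not shift it back by a transit time.

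Feces are the route by which the drug is expected to remove copper, so dilution with pre-treatment stool matters for:

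- the 15 mg accumulation component of the primary endpoint;
- its change from baseline (SAP 5.1.2 and 7.2.2);
- the exploratory duration endpoint, "Determine the effect of time following initiation of ALXN1840 treatment on copper balance" (Protocol Section 3), for which Days 1-8 against Days 25-28 is the natural comparison at a fixed dose;
- any dose comparison that draws on Days 1-8. SAP 7.2.3 sets treatment period 1 (15 mg) against treatment period 2 (30 mg) without naming the windows. In SAP Section 4, Treatment Period 2 starts at re-admission on Day 22 or 23 and so contains the 15 mg Days 25-28.

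**Working it through.** **The plan's own figure.** The mean of 33 h and 47 h is (33 + 47)/2 = 40 h = 1.67 days, which the plan rounds to about 2 days. The figures agree.

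**Assumption.** Stool reflects gut content one transit time (L days) earlier. This is the premise the plan uses when it lets Days 29-30 stool count for 15 mg.

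**Share of Days 1-8 holding pre-treatment stool.** The window is 8 x 24 = 192 h, so the share is transit hours/192. If the true fecal effect is constant from the first dose, Days 1-8 show (8 - L)/8 of it and Days 25-28 show all of it. The apparent ratio is then 8/(8 - L).

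| Transit | Share of Days 1-8 | Apparent ratio, Days 25-28 to Days 1-8 |
|---|---|---|
| 33 h (men) | 33/192 = 17.2% | 8/(8 - 1.375) = 1.21 |
| 40 h (average) | 40/192 = 20.8% | 8/(8 - 1.667) = 1.26 |
| 47 h (women) | 47/192 = 24.5% | 8/(8 - 1.958) = 1.32 |
| 48 h (two-day rule) | 48/192 = 25.0% | 8/(8 - 2) = 1.33 |

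If the last bowel movement falls on Day 7, the window shrinks to 168 h and the share rises to between 33/168 = 19.6% and 48/168 = 28.6%.

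**Days 31-35.** This window opens 48 h after the first 30 mg dose. At any transit up to 48 h it holds no stool from before the dose change.

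**Dose comparisons.** Suppose the effect is the same at both doses and the two 15 mg windows are pooled by day (8 + 4 = 12 days). The apparent 30 mg to 15 mg ratio is 12/(12 - L): 1.13 at 33 h, 1.16 at 40 h, 1.20 at 48 h. If only Days 1-8 stand for 15 mg, the ratios in the table apply. Days 25-28 against Days 36-39 gives 1.00, because neither window touches Day 1.

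**Scale, for illustration only.** Protocol 2.1 cites injected sheep whose fecal copper rose from about 3 to about 7 mg/day, an increment of 4. Days 1-8 would show 4 x (1 - 0.208) = 3.17 mg/day at 40 h, and 3.00 at 48 h.

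**Allowing for real accumulation.** Suppose the fecal effect builds as 1 - exp(-kt), with k = ln 2/2 per day. The 2-day half-life comes from the note in SAP 5.1.2; applying it to fecal output is an assumption. As a fraction of steady state:

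- Days 1-8, no lag: 1 - (1 - exp(-8k))/(8k) = 0.66
- Days 1-8, two-day lag: (6/8) x [1 - (1 - exp(-6k))/(6k)] = 0.75 x 0.58 = 0.43
- Days 3-8, two-day lag: 1 - (1 - exp(-6k))/(6k) = 0.58

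Under this model accumulation alone gives a rise of 1/0.66 = 1.5, which is larger than the lag alone. Removing the lag reduces the combined rise from 1/0.43 = 2.3 to 1/0.58 = 1.7. It does not bring it to 1.

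**After the change, constant effect.** Days 3-8 open 48 h after the first dose. They recover the whole effect at any transit up to 48 h, and the apparent ratio becomes 1.00.

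**The case against.** **Day 1 follows the definition.** The notes in Protocol Section 3 and SAP 5.1.2 run the accumulation period from the first dose on Day 1 to expected steady state at Day 10. Days 1-8 is the collected part of that interval. This stands as a reason to keep Days 1-8 in the report. It does not explain the asymmetry, because the note rests on a half-life, and on the same reasoning 30 mg accumulation would start on Day 29.

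**The exclusion rule is inferred.** A reader might infer that the plan formally removes Days 29-30 from the 30 mg windows because of transit. It does not say so. It gives no reason for opening on Day 31, and it only permits borrowing that stool for 15 mg. The point therefore rests on unequal treatment of the two transitions and on the general statement about transit, not on a stated exclusion rule that Day 1 breaks.

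**Direction.** The primary analysis seeks a net negative balance. Dilution makes Days 1-8 look less negative if the drug raises fecal copper, so it works against a false claim. This is correct for the primary aim. It does not help the duration question, where an attenuated early window exaggerates the later rise.

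**Descriptive and visible.** There is no hypothesis test, daily balance is plotted by participant and as a mean, and efficacy data are listed. A reader can look at Days 1-2. The tabulated period means are still uncorrected, and with about 10 participants those means are the main result.

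**Changing the window late.** This SAP covers the second and subsequent interim analyses of an open-label study. Replacing a primary window now would invite a post hoc criticism. That is a good reason to add a lagged summary and not to replace the existing one.

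**Conclusion.** The asymmetry is in both documents, and no other rule corrects it. At the plan's own transit times, 17-25% of Days 1-8 is pre-treatment stool. A true fecal effect in that window, and its change from baseline, is attenuated by that share. A constant effect would look 1.21 to 1.33 times larger in Days 25-28, and 1.26 times at 40 h. These figures rest on stool lagging gut content by one transit time and on an effect that is constant from the first dose.

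Three stronger readings are not supported:

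- That the plan creates a trend from nothing. The bias is proportional to a real fecal effect and is zero without one.
- That the dose response as a whole is distorted. The Days 25-28 versus Days 36-39 comparison is untouched. Only comparisons using Days 1-8 are affected, and SAP 7.2.3 does not say whether its period summary is one of them. A direct Days 1-8 versus Days 31-35 contrast is not a listed analysis, and those phases differ anyway because 30 mg accumulation starts from 15 mg steady state.
- That a lagged window would isolate the effect of duration. Genuine accumulation would remain in it.

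The point deserves correction because the duration question is one the study sets out to inform. It does not undermine the primary aim.

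**What to change.** In Protocol 9.4.1 and SAP 7.2.1:

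- Prespecify a transit-lagged 15 mg accumulation summary over Days 3-8.
- Report it beside Days 1-8 for the primary endpoint and for change from baseline.
- Use it for the duration comparison and for any dose comparison that includes the accumulation phase.
- Keep the Day 1 accumulation definition for plasma PK.
- State that the lagged window was added after an earlier interim analysis, and that a rise from Days 3-8 to Days 25-28 may still reflect real accumulation.

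In SAP 7.2.3, name the windows behind the treatment period 1 versus treatment period 2 summary.

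The cost is wording and one extra set of summaries, since every day is already collected. The lagged mean rests on six days instead of eight, still above the three-day minimum in Protocol 4.2. Days 1-2 intake and urine, which have no gut-transit lag, are left out of that summary, which is a further reason to keep Days 1-8 beside it.

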3. In this study, dosing for ALXN1840 will be initiated at 15 mg once daily for a minimum of 4 weeks, with an increase to 30 mg after 4 weeks, unless there are safety concerns that, in the opinion of the Investigator(s) and/or Alexion, may place participants at undue risk, in which case, patients may remain on the 15 mg/day dose for the duration of the study.	
 • Dose range limit 15 mg every other day to 30 mg/day
4. The dose should be decreased or interrupted if any of the relevant Dose Modification criteria are met (Table 7).	
 • Dose range limit 15 mg every other day to 30 mg/day

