9.4.1. Primary Analysis

The primary objective of this study is to demonstrate a net negative copper balance with daily repeat-dose ALXN1840 treatment (15 mg and 30 mg) in participants with WD.

The primary analysis will be performed using the Full Analysis Set. Average daily copper balance and molybdenum balance will be calculated over the following periods:

1. Day -4 through Day -1 representing predose baseline
2. Days 1 through 8 representing the ALXN1840 15 mg/day accumulation period
3. Days 25 through 28 representing the ALXN1840 15 mg/day steady-state period
4. Days 31 through 35, representing the ALXN1840 30 mg/day accumulation period
5. Days 36 through 39 representing the ALXN1840 30 mg/day steady-state period

As ALXN1840 is expected to increase copper excretion through fecal excretion, copper in stool will be critical for determining copper balance. Because stools can be irregular, assessment of copper and molybdenum balance will only include data up to the day of the final bowel movement. For example, for the period Day 1 through Day 8, if the final bowel movement occurs on Day 7, average daily copper balance for the Day 1 through Day 8 period will only include data from Day 1 through Day 7.

In the case of the 15 mg/day steady-state period (ie, Day 25 through Day 28), stool data collected on Days 29 - 30 samples may be used if needed to support assessments for the 15 mg/day dose. Use of these stool data (as needed) are consistent with an approximately 2-day gastrointestinal transit time.

In the case of stool irregularity, and to support assessment of copper output over time, bowel movement copper and molybdenum outputs may be averaged over the days between bowel movement (or start of study) to ensure an approximate value for each 24-hour period.

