6.3. Full Analysis Set

All participants who received at least 1 dose of ALXN1840 treatment.

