6.4. Per Protocol Set

All participants who received at least 1 dose of ALXN1840 treatment, had Baseline and all post-Baseline values of copper intake (in food and drink) and copper output (in feces and urine), and were 100% compliant with study drug dosing. Participants with important protocol deviations that are likely to impact the primary endpoint analysis will be excluded from the Per Protocol (PP) Set. Important protocol deviations and the PP Set will be defined, documented, and agreed within Alexion prior to database lock.

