7.3.1. Study Duration, Treatment Compliance, and Exposure

Study duration will be summarized for all enrolled participants by cohort and overall. Study duration is defined as the time from first dose to the EOS or study discontinuation date (whichever occurs first) + 1.

Compliance during the Inpatient and Outpatient periods will be determined as the days taken / the days expected to be taken during active study treatment x 100. Treatment compliance will be summarized using descriptive statistics within cohort and overall. If a subject prematurely discontinues, his or her compliance will be based on the period up to the point of discontinuation from the study. Compliance will also be summarized using counts and percentages by compliance category (ie, $\geq 100\%$ compliance, 80 to $<100\%$ compliance, 60 to $<80\%$ compliance, etc.). A supporting listing will also be produced.

Exposure will be summarized for the Safety Set by cohort and overall. The duration (days) of exposure to treatment for each period will be calculated as date of last exposure to treatment – date of first dose + 1. The actual duration of treatment will be calculated as the exposure period – number of days on which treatment was temporarily stopped. The duration of exposure, average daily dose (mg), minimum daily dose (mg) and maximum daily dose (mg) for each period (as described in Section 7.2.1), and overall, as applicable will be summarized using descriptive statistics. Listings of exposure, drug interruptions and missed doses will also be presented.

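### Balance windows carry a dose label fixed by nominal study day, so participants not taking the labelled dose would be averaged into the 15 mg/day and 30 mg/day means

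*SAP*

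**What the plan says.** The two 30 mg windows in SAP 7.2.1 are "Days 31 through 35 representing the ALXN1840 30 mg/day accumulation period" and "Days 36 through 39 representing the ALXN1840 30 mg/day steady-state period". Protocol 9.4.1 has the same list, including "Days 31 through 35, representing the ALXN1840 30 mg/day accumulation period". Days 1-8 and Days 25-28 are labelled 15 mg/day in the same way.

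The population is set without regard to dose: "The primary analysis will be performed using the FA Set", and that set (SAP 6.3) is "All participants who received at least 1 dose of ALXN1840 treatment". The primary endpoint (SAP 5.1.1) is mean daily copper balance in accumulation and steady-state periods at each dose level.

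Other doses are foreseen. Under Protocol 4.1, Table 4, feature 3, if there are safety concerns "patients may remain on the 15 mg/day dose for the duration of the study". Table 4 sets the lower limit at 15 mg every other day, and Table 7 sets out reductions and interruptions.

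The only sensitivity analysis (SAP 7.2.1.5) repeats the primary analysis on the Per Protocol Set. Among other conditions, its members must be those who "were 100% compliant with study drug dosing" (SAP 6.4). Compliance (SAP 7.3.1) "will be determined as the days taken / the days expected to be taken", as a percentage. The only data-handling rule for the primary analysis (SAP 7.2.1.1) concerns premature study discontinuation.

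**The concern.** An endpoint reported per dose should describe people taking that dose. Here the label follows the study day, and SAP 7.2.3 repeats the shortcut by naming treatment period 1 as 15 mg and treatment period 2 as 30 mg. Followed exactly, the plan puts 15 mg data under a 30 mg/day heading. A reduction or interruption before Day 28 would likewise put off-dose data into the 15 mg/day steady-state mean. Molybdenum balance uses the same windows.

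The situation is foreseeable. The Safety Review Committee meets to confirm the step to 30 mg (Protocol 9.7). Protocol Table 3 places dose-dependent transaminase elevations usually at 3 to 6 weeks of treatment, roughly Days 21-42, which spans the Day 25-39 collection. Table 7 ties dose changes to ALT.

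At stake is the stated purpose of separating a decoppering dose from a maintenance dose (Protocol 2.1), with about 10 participants and interim summaries meant to support regulatory submissions (SAP 4).

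**Working it through.** The plan has no figure of its own to reproduce here. The sample size of approximately 10 (SAP 9.1) comes without effect size, SD, alpha or power. The check traces the rules, then gives illustrative arithmetic.

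**Step 1. Does any rule tie a window to the dose taken?** SAP 7.2.1 uses days, SAP 6.3 requires one dose of any size, and SAP 7.2.1.1 covers only study discontinuation. SAP 7.3.1 summarises average, minimum and maximum daily dose per period, but as exposure. By contrast, SAP 7.4.1 and 7.4.2 summarise PK and PD concentrations by dose as well as day. So no such rule exists for balance.

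**Step 2. Would the Per Protocol Set remove these participants?** Compliance = days taken / days expected × 100. Assume Days 1-39 and no outpatient extension.
- 15 mg daily throughout: 39/39 = 100%. Staying on 15 mg is a permitted adaptive feature needing no amendment, so on its face it is not a deviation.
- 15 mg every other day from Day 29 (illustrative timing): doses on Days 29, 31, 33, 35, 37 and 39, so 28 + 6 = 34 days taken. If days expected follow the prescribed schedule, 34/34 = 100%. If every day is expected, 34/39 = 87.2%. The SAP does not say which applies.

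**Step 3. What dose would the 30 mg/day row represent?** Let n = 10 and let k be the number not on 30 mg; k is an assumption, shown for 1 to 3. Mean dose = [30(n − k) + d·k]/n, where d = 15 mg/day for daily dosing and 7.5 mg/day for every-other-day dosing (2 × 15 mg over Days 36-39 = 30/4).

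| k | Others on 15 mg daily | Others on 15 mg every other day |
|---|---|---|
| 1 | 28.5 mg/day | 27.75 mg/day |
| 2 | 27.0 mg/day | 25.5 mg/day |
| 3 | 25.5 mg/day | 23.25 mg/day |

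**Step 4. Effect on the 30-versus-15 mg contrast.** Let B30 and B15 be the mean balances at the two doses. Assume the k participants stay on 15 mg daily, respond like the others, and show no change in balance between Days 25-28 and the later windows. Then:

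[(n − k)·B30 + k·B15]/n − B15 = (1 − k/n)(B30 − B15)

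For n = 10 and k = 1, 2, 3, the share retained is 0.9, 0.8, 0.7, a loss of 10%, 20% or 30%. Summaries are also given by cohort (SAP 7). In an assumed cohort of 5 the same k leaves 80%, 60% or 40%. The formula does not cover participants whose dose is reduced or interrupted between the two windows, because balance at those doses is unknown.

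**The case against.** The best defence is that little is hidden and nothing is tested. The study is exploratory and descriptive (SAP 7.2.1.4), so no error rate or decision rule is affected. Efficacy listings (SAP 7.2), a daily balance plot for each participant (7.2.1), a boxplot with individual points (7.2.3), and dose summaries and interruption listings (7.3.1) would expose an off-dose participant. The shrinkage in Step 4 concerns an exploratory contrast, not the primary endpoint. All of that stands and limits the severity, but none of it corrects the labelled mean.

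Selection cuts the other way. Averaging all treated participants does not select; restricting the 30 mg rows to those who escalated does. This also stands, and it is why the by-day table must remain.

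Four stronger readings are tempting but unsupported:
- **That about 2 of 10 would not escalate.** A reader might infer this from the Phase 2 figure of 6 of 28 (21%) on 15 mg in Protocol 4.3. That is the dose at Week 24 or at last dose under individual titration on safety, corrected NCC and symptoms (Protocol 2.2). It says nothing about safety-based non-escalation at Day 29.
- **That the Per Protocol Set is bound to keep these participants.** Important deviations and the set itself are settled before database lock (SAP 6.4), so the sponsor could exclude them. SAP 6.4 does not cite the days-based formula, and Protocol 6.4 assesses outpatient compliance by tablet counts. The text does not require exclusion; it does not forbid it.
- **That counting milligrams taken against milligrams prescribed would cure it.** A participant prescribed 15 mg who takes 15 mg still scores 100%.
- **That a 30 mg steady-state row should require the full time to steady state at 30 mg.** Days 36-39 are days 8 to 11 of that dose (36 − 29 + 1 = 8; 39 − 29 + 1 = 11), against 10 days in the note to Protocol section 3 and 10 to 12 in 2.2. Such a condition could disqualify participants who escalated on schedule.

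**Conclusion.** The gap is real. It is a stated rule that can yield a mislabelled mean, rather than an omitted detail. Any participant on a permitted dose other than the labelled one would be averaged into the 15 mg/day or 30 mg/day copper and molybdenum means, and the Per Protocol analysis need not remove them. That is clear for 15 mg daily; for every-other-day dosing it turns on how days expected is read.

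The size cannot be fixed from the documents. The 10% to 30% loss of contrast rests on an assumed 1 to 3 of 10 not escalated, a common dose effect and no time trend, and time on treatment is itself an exploratory question. If everyone escalates on Day 29 and no dose is modified, this problem does not arise.

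A reader might infer that the primary results would be invalid. The documents do not support that: the analysis is descriptive and affected participants would be visible. This is a should-fix.

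**What to change.** In SAP 7.2.1 to 7.2.3:
- Report dose-labelled means for participants who, per dosing records, received the labelled dose from its scheduled start (Day 1 for 15 mg, Day 29 for 30 mg) through the window.
- Show participants on any other regimen in a separate row or listing.
- Keep the all-Full-Analysis-Set table by study day alongside.
- Present the 30-versus-15 mg comparison within participants who have both windows at the labelled doses.

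If the Per Protocol Set is meant to support dose-specific means, SAP 6.4 should require receipt of the labelled dose in each window.

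The cost is SAP wording and a derived dose-received flag from records that Protocol 6.4 already requires, including dates of dose reductions. The downside is a smaller n in the 30 mg rows and restriction to those who tolerated escalation, which is why the all-participant table stays. The rule should be set before results are seen. No change to any dosing rule is proposed.
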